9.4.4.1 Items

ECG interpretation, heart rate, PR, QRS, QT, QTcB, and QTcF.

(QTcB and QTcF which are calculated at site will not be used for analyses and will be presented on the listing only.)

QTcB and QTcF will be calculated using the following formulas:

- $QTcB = QT / (RR^{0.5})$
 - $QTcF = QT / (RR^{0.33})$
- where $RR = 60 / \text{heart rate (bpm)}$

9.4.4.2 Methods

The following table will be prepared for ECG interpretation:

- Shift table of ECG interpretation by visit (Safety analysis set)

The following tables and figures will be prepared for heart rate, PR, QRS, QT, QTcB, and QTcF:

- Summary of maximum/minimum post-baseline values for 12-lead ECGs (Safety analysis set)
- Line plot of 12-lead ECGs by subject (Safety analysis set)

The following tables will be prepared for QT, QTcB, and QTcF:

- Category of QT, QTcB, and QTcF by visit (Safety analysis set)
- Category of change from baseline of QT, QTcB, and QTcF by visit (Safety analysis set)

The categories of QT, QTcB, and QTcF are as follows:

- ≤ 450 msec; $450 < , \leq 480$ msec; $480 < , \leq 500$ msec; > 500 msec

The categories of change from baseline of QT, QTcB, and QTcF are as follows:

- ≤ 30 msec; $30 < , \leq 60$ msec; > 60 msec

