### **1.3.3 Safety Pharmacology**

In exploratory safety pharmacology studies, MLN2238 was a weak inhibitor of the cloned cardiac potassium ( $K^+$ ) human ether à-go-go-related gene (hERG) channel, with an  $IC_{50}$  of 59.6  $\mu\text{M}$ , which exceeds, by approximately 200-fold, the plasma  $C_{\text{max}}$  (111 ng/mL [0.3  $\mu\text{M}$ ]) predicted to occur in humans at the optimally efficacious dose after IV administration.

In the Good Laboratory Practice (GLP) compliant, 1-cycle, repeat-dose, PO toxicology study in beagle dogs, an increase in corrected QT interval (QTc) was seen in male dogs at nontolerated doses, and a potential increase in QTc was seen in male dogs at tolerated doses. However, increased QTc was not seen in female dogs at any dose, despite the fact that female dogs had plasma  $C_{\text{max}}$  values similar to those of male dogs. Additionally, in a GLP-compliant, 2-cycle, repeat-dose, IV toxicology study in beagle dogs, no increase in QTc was seen in either male or female dogs at any dose, even though dogs in the IV study had higher plasma MLN2238 concentration values than did the male dogs in the PO study. These data suggest that MLN2238 has a low potential for prolonging the QT interval in vivo. In the GLP-compliant, repeat-dose toxicology studies in beagle dogs, no effects on clinical signs or physical examination findings indicative of impaired respiratory or CNS function were noted at tolerated doses ( $\leq 0.14 \text{ mg/kg}$ ) after IV or PO administration. Detailed neurologic examinations MLN2238-related changes in neurologic parameters, primarily observed as changes in mental status (very low arousal) and changes in gait (ataxia) were observed at nontolerated doses ( $\geq 0.18 \text{ mg/kg}$ ). Similar findings were not observed at tolerated doses with any consistency.

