## 10. STATISTICAL CONSIDERATIONS

### 10.1 Endpoints and Analysis Set

#### 10.1.1 Primary Endpoint

- DLTs, adverse events, body weight, vital signs, 12-lead ECGs, laboratory tests
- MLN2238 plasma concentration

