### **10.4 Statistical Methods of Analysis**

The demographic data and all endpoints data will be analyzed. Summary statistics (numbers of subjects, mean, median, standard deviation, maximum, minimum) will be calculated for continuous data. Frequencies and proportions will be tabulated for categorical data.

Details are presented in the statistical analysis plan.

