6. STUDY ENDPOINTS

6.1 Primary Endpoint

- DLTs, adverse events, body weight, vital signs, 12-lead electrocardiograms (ECGs), laboratory tests.
- MLN2238 plasma concentration.

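### The SAP plans no summary of QTc change from baseline on the continuous scale, and the tables it does plan are insensitive to a mean shift of 10 to 20 msec

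*SAP*

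**What the plan says.** Both documents place ECGs in the primary endpoint: Protocol 10.1.1 lists "DLTs, adverse events, body weight, vital signs, 12-lead ECGs, laboratory tests", and SAP 6.1 has the same list.

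SAP 9.4.4.2 names these ECG outputs:

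- a shift table of the ECG interpretation;
- "Summary of maximum/minimum post-baseline values for 12-lead ECGs (Safety analysis set", covering heart rate, PR, QRS, QT, QTcB and QTcF;
- "Line plot of 12-lead ECGs by subject (Safety analysis set", covering the same six variables;
- a by-visit table of absolute QT, QTcB and QTcF in four bands, cut at 450, 480 and 500 msec;
- "Category of change from baseline of QT, QTcB, and QTcF by visit (Safety analysis set", in three bands: up to 30, above 30 to 60, and above 60 msec.

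SAP section 10 adds a listing of the individual 12-lead ECG data.

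As a general rule, Protocol 10.4 states "Summary statistics (numbers of subjects, mean, median, standard deviation, maximum, minimum) will be calculated for continuous data", and SAP 9.1 repeats it. For ECGs in particular, Protocol 10.4.1.4 says only that they will be summarised. Continuous change-from-baseline statistics are promised in Protocol 10.4.1.3, for laboratory tests.

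The schedule in Protocol 7.2.2 gives a predose ECG on Cycle 1 Day 1, then ECGs on Day 15 at predose, 30 minutes, 1 hour and 4 hours, and one at 24 hours on Day 16. Protocol 7.2.3 adds one at the end-of-study visit.

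**The concern.** QTc is continuous and is measured at a planned series of times around the Day 15 dose. Its change is nevertheless tabulated only after being cut into three bands, and the lowest band pools every decrease with every increase up to 30 msec. A moderate shift shared by most subjects would leave nearly all of them in that band.

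The one numerical table on the continuous scale does not fill the gap. It reports each subject's extreme post-baseline values, without reference to baseline or time after dose.

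At stake is how this part of the primary safety endpoint is reported. With no planned mean change, a statement about QTc would rest on an insensitive table, on reading individual plots by eye, or on a calculation chosen after the data are seen. Protocol 1.3.3 gives some reason to look: after oral dosing "a potential increase in QTc was seen in male dogs at tolerated doses", although the same section goes on to conclude that the potential for QT prolongation is low.

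**Working it through.** **The plan's own figure.** Four cohorts of 3 to 6 subjects: 4 × 3 = 12 and 4 × 6 = 24, which agrees with Protocol 10.2 and SAP 5.2. There is no alpha, power or QTc effect size to reproduce.

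**Inputs.** The cut points come from SAP 9.4.4.2 and the group sizes from SAP 5.2. The SD of an individual QTc change is in neither document. It is assumed here to lie between 10 and 25 msec, with changes normally distributed.

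**Step 1: share of subjects in the lowest band.** P = Φ((30 − mean shift) / SD). For example, a 10 msec shift with SD 15 gives Φ(20/15) = 0.909.

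| True mean shift | SD 10 | SD 15 | SD 20 | SD 25 |
|---|---|---|---|---|
| 0 msec | 99.9% | 98% | 93% | 88% |
| 10 msec | 98% | 91% | 84% | 79% |
| 15 msec | 93% | 84% | 77% | 73% |
| 20 msec | 84% | 75% | 69% | 66% |

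For shifts of 10 to 20 msec the range is 66% to 98%.

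**Step 2: what the table would show at SD 15.** The expected number above 30 msec is n(1 − P). The chance that nobody exceeds 30 msec is P to the power n.

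| True mean shift | n = 3 | n = 6 | n = 12 | n = 24 |
|---|---|---|---|---|
| 0 msec | 0.07; 93% | 0.14; 87% | 0.27; 76% | 0.55; 58% |
| 10 msec | 0.27; 75% | 0.55; 56% | 1.09; 32% | 2.19; 10% |
| 20 msec | 0.76; 42% | 1.51; 17% | 3.03; 3% | 6.06; 0.1% |

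In a cohort of 3 to 6, an empty upper band is the more likely result both with no shift and with a 10 msec shift. With 24 subjects pooled, a 20 msec shift would usually show as an excess (about 6 subjects against 0.5).

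**Step 3: the table of extremes.** The schedule gives six post-baseline ECGs: four on Day 15, one at 24 hours and one at end of study. The expected maximum of six independent normal readings lies 1.27 within-subject SDs above their mean with no drug effect (1,000,000 simulated draws). At an assumed within-subject SD of 10 msec that is 1.27 × 10 = 12.7 msec, as large as the shift in question.

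**Step 4: what a mean-change table would deliver.** The half-width of a two-sided 90% interval is t(0.95, n − 1) × SD / √n.

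| Assumed SD | n = 3 | n = 6 | n = 12 | n = 24 |
|---|---|---|---|---|
| 10 msec | 16.9 | 8.2 | 5.2 | 3.5 |
| 15 msec | 25.3 | 12.3 | 7.8 | 5.2 |
| 20 msec | 33.7 | 16.5 | 10.4 | 7.0 |

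**The case against.** The strongest reply is that nothing is lost. By-subject line plots and the ECG listing keep every QTc value, and with 12 to 24 subjects a consistent shift could be seen in the plots or calculated from the listing. This stands against any inference that the planned ECG output cannot show a shift. What is missing is a planned numerical summary of it.

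A reader might also infer a breach of Protocol 10.4. The text does not support that. The rule asks for summary statistics of continuous data without mentioning change, the table of extremes can be read as applying it to ECG values, and continuous change is promised only for laboratory tests.

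A third temptation is to measure the loss as a difference in power between a test on the mean and a test on the count above 30 msec. The plan contains no QTc test, the sample size has no statistical rationale, and a count test in such small groups runs well below its nominal level, which exaggerates the contrast.

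The nonclinical signal should not be over-read either. Protocol 1.3.3 also reports no QTc increase in female dogs at similar peak concentrations, none in the intravenous study at higher concentrations, and a hERG margin of about 200-fold.

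Nor can it be said that the plan omits a concentration-QTc analysis. The Pharmacokinetics Analysis Plan (SAP Appendix A) is not in the text available.

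Finally, the remedy cannot resolve a 10 to 20 msec shift in a cohort of 3. That is correct, and it limits what the new table may be used for.

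**Conclusion.** The point holds as a gap in the planned summaries. SAP 9.4.4.2 names no continuous change-from-baseline summary for QTcF, QTcB or QT. Its change table would leave 66% to 98% of subjects in the lowest band under a true mean shift of 10 to 20 msec. Its table of extremes is not a change, and its maximum is biased upward. The planned tables are therefore insensitive to such a shift, most clearly at 10 msec within a cohort of 3 to 6, and only the line plots and listing would reveal it.

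The sizes rest on normality and on SDs assumed by this review. The bias of the maximum also assumes independent readings. The gap itself rests on the SAP text alone. This is an inexpensive descriptive improvement; it does not mean that the ECG endpoint goes unanswered.

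**What to change.** Add to SAP 9.4.4.2, for example:

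> Change from baseline in QTcF, QTcB, QT, heart rate, PR and QRS will be summarised at each nominal ECG time (Cycle 1 Day 15 predose, 30 min, 1 h, 4 h and 24 h; end of study) with n, mean, SD, median, minimum, maximum and a two-sided 90% confidence interval for the mean, by treatment group and in total. These summaries are descriptive.

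Keep the category tables as the outlier display.

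The cost is one paragraph and one table from ECGs already scheduled, with no new procedures or subjects. There are two limits to state beside the table. With no control group, the mean change includes effects that are not due to the drug. Precision is also coarse in small groups: at the assumed SD of 15 msec the 90% half-width is about 25 msec at n = 3, 12 at n = 6, 8 at n = 12 and 5 at n = 24. The table is therefore mainly useful for pooled groups, and 12 to 24 subjects will be available only if all four cohorts are studied, which Protocol 3.1 does not guarantee.

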9.4.5 Vital Signs

9.4.5.1 Items

Temperature, pulse, systolic blood pressure, diastolic blood pressure, SpO₂, and weight.

9.4.5.2 Methods

The following tables and figures will be prepared for each item:

- Summary of maximum/minimum post-baseline values for vital signs (Safety analysis set)
- Summary of maximum/minimum post-baseline values for weight (Safety analysis set)
- Line plot of vital signs by subject (Safety analysis set)
- Line plot of weight by subject (Safety analysis set)

9.4.6 Eastern Cooperative Oncology Group (ECOG) Performance Status

9.4.6.1 Items

ECOG performance status.

9.4.6.2 Methods

The following table will be prepared:

- Eastern Cooperative Oncology Group performance status by visit (Safety analysis set)

9.5 Efficacy Analyses

9.5.1 Tumor Response

Tumor response will be assessed using the International uniform response criteria for multiple myeloma (Durie et al, 2006).

Maximum M-protein change is the largest percent change from baseline among all post-baseline measures of the Total M-protein. For subjects with measurable serum M-protein at baseline, it is the percent change from baseline to the best (lowest) post-baseline value in serum M-protein. For subjects with non-measurable serum M-protein but measurable urine M-protein at baseline, it is the percent change from baseline to the best (lowest) post-baseline value in urine M-protein.

9.5.1.2 Methods

For all items, the following table will be prepared using Response Evaluable Analysis Set:

- Summary of Tumor Response (Response Evaluable Analysis Set).

For ORR, frequencies and percentages with 2-sided 95% exact confidence interval using the F distribution method given in Collett (2002) will be presented.

DOR, time to response, and TTP will be summarized descriptively. For DOR and TTP, Kaplan-Meier method will be used.

For best response and maximum M-protein change, frequencies and percentages will be presented by category.

10. LISTING

- Deaths on study
- Treatment-emergent adverse events
- Treatment-related adverse events
- Serious adverse events
- Adverse events leading to permanent discontinuation of study treatment
- Dose limiting toxicities by safety evaluation committee in cycle 1
- Dose limiting toxicities by investigator
- Hematology
- Chemistry (including corrected calcium)
- Urinalysis
- Beta-2-microglobulin
- Serum free light chain
- Serum M-protein
- Serum immunofixation
- Quantitative immunoglobulins
- Spot urine M-protein
- 24-hour urine M-protein
- Urine immunofixation
- Bone marrow evaluations: Aspiration

- Chest X-ray
- Skeletal survey
- CT/MRI
- Plasmacytoma evaluation
- Vital signs
- Pregnancy test
- 12-lead ECGs
- Eastern Cooperative Oncology Group performance status
- Subject disposition (including informed consent for extended administration)
- Screen failures
- Important protocol deviations
- Analysis sets
- Demographics
- Medical and surgical history
- Disease characteristics
- Prior therapy
- Prior radiation therapy
- Prior transplant procedure
- Prior surgery
- Tumor response (Investigator response assessment)
- Overall efficacy
- Summary of exposure to MLN9708
- Summary of exposure to Lenalidomide
- Summary of exposure to Dexamethasone
- Exposure to MLN9708 by visit
- Exposure to Lenalidomide by visit
- Exposure to Dexamethasone by visit
- Concomitant medications
- Concomitant procedures
- Grade 3 or higher clinical laboratory abnormalities

11. APENDICES

- Appendix A: Pharmacokinetics Analysis Plan

13. DOCUMENT HISTORY

Version	Date	Author	Remarks
1.0	11 April 2012	PPD	Original version
2.0	12 February 2014	PPD	
"BSA" and "EOS" have been added to the list in section 1.
 
Description of the study design has been corrected in section 5.1.
 
Some descriptions have been corrected in section 7, 8, and 9.
 
"8.2 Handling of Partial Date" has been added in section 8.
 
"total of monotherapy treatment groups" and "total of combination treatment groups" have been deleted in section 9.1.
 
To use "International uniform response criteria for multiple myeloma (Durie et al, 2006)" for evaluating the tumor response has been added in section 9.1.
 
"MLN9708 completion", "Lenalidomide completion", "Dexamethasone completion", and "Study completion" have been deleted from items for subject disposition in section 9.2.1.1.
 
"Study treatment completion" has been added to items for subject disposition in section 9.2.1.1.
 
"Study status" has been added to items for subject disposition in section 9.2.1.1.
 
Methods have been changed in section 9.2.1.2.
 
"BSA" and formula for calculating it have been added to items for demographic and baseline characteristics in section 9.3.1.1.
 
"Duration from last prior antineoplastic therapy to first dose", "Duration from last prior radiation therapy to first dose", "Duration from last prior bone marrow transplant or stem cell transplant to first dose", "Duration from last prior any surgical procedures to first dose", and formula for calculating them have been added to items for disease characteristics in section 9.3.1.1.
 
"Evidence of lytic bone disease" has been changed to "Evidence of lytic bone disease at initial diagnosis" in section 9.3.1.1.
 
"Evidence of extramedullary disease" has been changed to "Evidence of extramedullary disease at initial diagnosis" in section 9.3.1.1.
 
"Serum creatinine and by category" has been deleted

			
in section 9.3.1.1.
 
"Serum creatinine (in summary statistics)" and "Serum creatinine by category" have been added in section 9.3.1.1.
 
The Cockcroft-Gault formulas for calculating creatinine clearance have been added in section 9.3.1.1.
 
"Detection of M-protein" has been deleted from items for disease characteristics in section 9.3.1.1.
 
"Kappa/Lambda ratio" has been changed to "Kappa/Lambda ratio by category" in section 9.3.1.1.
 
"Serum M-protein" has been changed to "Serum M-protein (total M-protein)" in section 9.3.1.1.
 
"Urine M-protein" has been changed to "24 hour urine M-protein (urine total M-protein)" in section 9.3.1.1.
 
"β₂-microglobulin by category" has been changed to "Beta-2-microglobulin by category" in section 9.3.1.1.
 
"Serum albumin by category" has been changed to "Albumin by category" in section 9.3.1.1.
 
Formulas for calculating corrected calcium have been added in section 9.3.1.1.
 
"Number of subjects with bone marrow aspirate" has been changed to "Subjects with bone marrow aspirate" in section 9.3.1.1.
 
"Bone marrow aspirate results" has been changed to "Bone marrow aspirate results (% Plasma cells)" in section 9.3.1.1.
 
"Skeletal survey results" has been changed to "Skeletal survey results at screening" in section 9.3.1.1.
 
"Lytic bone lesions at screening" has been added in section 9.3.1.1.
 
"Chest X-Ray results" has been changed to "Chest X-Ray results at screening" in section 9.3.1.1.
 
"MRI/CT results" has been changed to "CT/MRI results at screening" in section 9.3.1.1.
 
"Plasmacytomas at screening" has been added in section 9.3.1.1.
 
"Number of prior antineoplastic therapy" has been deleted in section 9.3.1.1.
 
"Prior antineoplastic therapy" has been added in section 9.3.1.1.
 
Items for concomitant medications have been deleted in section 9.3.1.1.
 
Methods have been changed in section 9.3.1.2.
 
"Number of doses taken" has been added in section 9.4.1.1.
 
Formulas for calculating dose intensity, relative dose intensity, and dosing compliance have been added in

--	--	--	--

		
section 9.4.1.1.
 
Definition for dose expected has been added in section 9.4.1.1.
 
The MedDRA version 15.0 for coding all adverse events to a SOC and a PT has been changed to version 16.0 in section 9.4.2.2.
 
To use "The textbook range (Pagana KD and Pagana TJ, 2011)" for grading of differential has been added in section 9.4.3.2.
 
"Subject incidence of hematology abnormalities by grade (Safety analysis set)" has been changed to "Subject incidence of hematology abnormalities at post-baseline by grade (Safety analysis set)" in section 9.4.3.2.
 
"Subject incidence of chemistry abnormalities by grade (Safety analysis set)" has been changed to "Subject incidence of chemistry abnormalities at post-baseline by grade (Safety analysis set)" in section 9.4.3.2.
 
"Subject incidence of urinalysis abnormalities by grade (Safety analysis set)" has been changed to "Subject incidence of urinalysis abnormalities at post-baseline by grade (Safety analysis set)" in section 9.4.3.2.
 
"Shift table of urinalysis (Safety Analysis Set)" has been changed to "Shift table of urinalysis by visit (Safety Analysis Set)" in section 9.4.3.2.
 
"RR" has been deleted from items in section 9.4.4.1.
 
Formulas for calculating QTcB and QTcF have been added in section 9.4.4.1.
 
Definitions for "ORR", "DOR", "time to response", "TTP", "Best response", and "Maximum M-protein change" have been changed in section 9.5.1.1.
 
Methods for "ORR", "DOR", "time to response", "TTP", "Best response", and "Maximum M-protein change" have been changed in section 9.5.1.2.
 
"Adverse events" has been deleted in section 10.
 
"Treatment-emergent adverse events" has been added in section 10.
 
"Adverse events leading to permanent discontinuation of investigational product" has been changed to "Adverse events leading to permanent discontinuation of study treatment" in section 10.
 
"Dose limiting toxicities" has been deleted in section 10.
 
"Dose limiting toxicities by safety evaluation committee in cycle 1" and "Dose limiting toxicities by investigator" have been added in section 10.
 
"Chemistry" has been changed to "Chemistry (including corrected calcium)" in section 10.
 
"Urine M-protein" has been deleted in section 10.
 
"Spot urine M-protein" and "24-hour urine M-

--	--	--

			
protein" have been added in section 10.
 
"Pregnancy test" has been added in section 10.
 
"Subject disposition" has been changed to "Subject disposition (including informed consent for extended administration)" in section 10.
 
"Prior radiation" has been changed to "Prior radiation therapy" in section 10.
 
"Investigator response assessment (IMWG)" has been changed to "Tumor response (Investigator response assessment)" in section 10.
 
"Overall efficacy" has been added in section 10.
 
"Concomitant medications" has been added in section 10.
 
"Concomitant procedures" has been added in section 10.
 
"Summary of tumor response" has been deleted in section 10.
 
"MLN9708 dosing" has been changed to "Exposure to MLN9708 by visit" in section 10.
 
"Lenalidomide dosing" has been changed to "Exposure to Lenalidomide by visit" in section 10.
 
"Dexamethasone dosing" has been changed to "Exposure to Dexamethasone by visit" in section 10.
 
"Bone marrow evaluations" has been changed to "Bone marrow evaluations: Aspiration" in section 10.
 
"β2-microglobulin" has been changed to "Beta-2-microglobulin" in section 10.
 
"12-Lead Electrocardiograms" has been changed to "12-lead ECGs" in section 10.
 
"ECOG performance status" has been changed to "Eastern Cooperative Oncology Group performance status" in section 10.
 
"Grade 3 or higher clinical laboratory abnormalities" has been added in section 10.
 
The section "12 REFERENCES" has been added.

--	--	--	--
